The proportion of treatment steps and not the incidence of medical error is taken as the unit of analysis, the reason for this is the high incidence of medical error that can even manifest itself with more than one error due to crisis, therefore, if used the incidence of the event would decrease the sample size.

Based on the study by Arraiga et al., The proportion of missed treatment steps in the expected control group is 26% and we consider a further 10% reduction in the intervention group to be clinically important. A minimum of 10% additional reduction in omitting treatment steps is decided because it is the approximate effect size of the other dimensions of non-technical skills other than resource management, a dimension that includes the use of checklists. It also establishes power of 90% and alpha of 0.05.

The sample calculation is then carried out in the analysis unit omitting treatment steps according to the formula:

$$n = \frac{\left[Z_{*} * \sqrt{2p(1-p)} + Z_{p} * \sqrt{p_{1}(1-p_{1}) + p_{2}(1-p_{2})}\right]^{2}}{(p_{1}-p_{2})}$$

With the statistical program R version 4.0.0 epiR statistical package, with the following code:

> library (epiR)

> epi.propsize (treat = 0.16, control = 0.26, n = NA, power = 0.9, design = 1, sided.test = 2, conf.level = 0.95)

We found a sample size of 492 treatment actions per arm, which corresponds to 984 in total, and with an estimate of student losses of 20%, we found the total of 1,180 treatment actions; Since 21 treatment steps are evaluated in each team, we obtain a total of 56 final semester medical students, 28 in each arm.

15. Recruitment

In order to complete the calculated sample size, the following recruitment strategies will be carried out:

- Explanation of the project at least once per internship cohort with the whole group.
- Request for participation on day 1 of the anesthesiology rotation in boarding school and the care rotation of the critically ill patient.

Table 8. Monthly evaluation of the monitoring status

Recruitment month	one	2	3	4	5	6	7	8
Current current income								
Income to date								
Income goal to date								
Real less projected								
Success ratio								
Projected final income								
Final deficit or excess								

IV Methods: allocation of interventions

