The theoretical exam, with no limit of attempts, must be 100% passed. This will be designed by the main researchers and approved by a teacher external to the study.

Protocol for the simulation sessions: based on the strategy of directed reflection, debriefing with good judgment, described by Maestre and collaborators(38); A safe container will be made, that is, the explanation of a series of agreements to generate confidence in the high-fidelity simulation, by a teacher trained in directed reflection in all the simulation days, with ample and sufficient explanation to ensure the greatest student participation based on three principles.

Denomination principle 1: fiction; both the researchers and the participants will commit to the best of their abilities to carry out the diagnoses and interventions as if it were a real patient; the simulation scenario will have physical fidelity, that is, spaces and sizes similar to real life. Emotional and psychological fidelity, that is, the same roles will be presented as in real practice; for example, treating doctor, nursing assistant and head of nursing to ensure that the perception of the situation is as close as possible to real life.

Denomination principle 2: confidentiality; All the actions carried out in the simulation sessions, both training and outcome measurement, will only be discussed in the reflection space directed at the end of each simulation among the participants and will not be commented on in other scenarios.

Denomination principle 3: basic principle; It will be verbally expressed that all the participants in the level of training in which they are considered to be competent, intelligent, who want to carry out the best actions to treat their patients and improve.

After the agreement of the safe container, that is, the explanation of the three previous principles will proceed with the description of the clinical scenario of two of the crises described at random. After that, the reflection will be carried out to checklists or training of non-technical skills according to the group.

Protocol for directed and structured reflection: directed reflection after the simulated crisis will last for a minimum of 30 minutes and a maximum of one hour, will consist of the following moments or phases:

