Phase 1: context description; After the simulation is finished, the participants will be transferred to the reflection room, a suitable and comfortable space different from the simulation. In this scenario, the phases of reflection will be described.

Phase 2: emotional discharge; Participants will be asked about the emotions experienced in the simulation of the crisis, in order to reduce the emotional burden that may arise and in addition to using the possible mental models described to direct the reflection.

Phase 3: discussion of reflection objectives: the objectives of the reflection will be described and agreed according to the intervention group, non-technical skills or checklists.

Phase 4: discussion about mental models, conclusions and learning from the session; It will be done through the use of the "molecule" (38) as an investigation strategy in the reflection with good judgment in order to clarify the actions, concepts and mental models related to the assigned group.

The exploration of mental models through the "molecule" strategy consists of the teacher or instructor, who uses the simulation with good judgment, carry out a directed dialogue to obtain an explanation by the student of an action committed in the simulation. This may be an error or a correct action, said explanation allows clarification or confirmation, by the teacher, of the concepts issued by the student.

The "molecule" is an interrogation strategy that, based on trust between the student and the teacher, allows the search for the reasons why a particular action was carried out(38).

For the intervention group

Since the effectiveness of a single day of intervention to improve non-technical skills in work teams is controversial (39)(40), the specific training in non-technical skills with guided reflection structured in a 10-hour program is proposed. Two hours on the teleeducation platform that includes a description of non-technical skills and checklists, reflection exercises, a pre-test and a test at the end of the platform's content; and 8 face-to-face hours in high-fidelity simulation divided into two four-hour days with a minimum of three days apart, which will emphasize directed and structured reflection (structured debriefing) to mental models that are related to non-technical skills according to the previously described simulation protocol.

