10 hour program; two hours on the teleeducation platform that includes a description of the checklists to be used, reflection exercises with a previous test and a test at the end of the contents of the platform focused on checklists; and 8 face-to-face hours in high-fidelity simulation divided into two four-hour days with a minimum of three days of difference between them, in which directed and structured reflection (structured debriefing) will be emphasized to the mental models that are related to the checklists. In crisis.

The training will be carried out with four random crises from the list of the pathologies described, two in each session, this in order to avoid cognitive continuity bias.

To achieve the correct use of the checklist in crisis, directed and structured reflection will be carried out so that the participants acquire the following behaviors

- Choosing the right list for the stage
- Assignment of a specific participant using the checklist
- Feedback to the work team on each action suggested in the checklist

For the present protocol, the checklists in Spanish of the Colombian Society of Anesthesiology SCARE that are freely available will be used during the development of simulation crises.(41).

Recording for measurement of outcomes:

The measurement of the outcomes described in section 18, will be carried out after completing the training, on a day different from the last simulation session. To guarantee the homogeneity of the treatment teams, each participant will be evaluated separately in a group of four people where three are resident doctors trained in non-technical skills and checklists blinded to the intervention, since they do not participate in the training sessions. , who will assume the roles of two nursing assistants and a circulator.

Three crises will be carried out at random, different from those used in training to avoid cognitive continuity bias and will be recorded in the same simulation center for all participants with a Logitech[®] brand HD camera reference Pro stream C922 using a Jabra brand microphone [®] reference Speak 510Ms.

For all cases after recording for outcome measurement:

As the intervention and control are about educational strategies of problem solving skills in medical crises, in simulated environments in students from the same year of training, from

a single center, in which it is not possible to blind the participant, there may be communication between treatment and control groups.

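### If students are trained in shared sessions, as Section 11a suggests, the planned tests ignore correlation between students trained together and the intervals would be too narrow

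*Combined protocol and SAP*

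**What the plan says.** **Randomisation.** Section 16a allocates individual students 1:1 in blocks of 2 and 4, without strata.

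**Training.** Under Section 11a each arm has two four-hour simulation days at least three days apart, with two crises per session. The debriefing content is set by arm, so any one training session belongs to one arm. Several phrases point to students training together:
- What happens in the sessions "will only be discussed in the reflection space directed at the end of each simulation among the participants".
- Phase 1 of the reflection protocol says "After the simulation is finished, the participants will be transferred to the reflection room".
- A target behaviour in both arms is "Assignment of a specific participant using the checklist", and another is feedback to the work team.

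**Outcome recording.** This is described differently: "each participant will be evaluated separately in a group of four people", the other three being resident doctors.

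**Sample size.** Section 14 counts treatment steps, and its code sets "design = 1, sided.test = 2, conf.level = 0.95", so the design effect is 1.

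**Analysis.** Table 9 uses a chi-square test on pooled steps for the primary outcome, and t, Fisher or chi-square tests for the rest. Section 20a promises to verify independence before parametric tests and offers non-parametric inference as the fallback. Section 20b rules out adjustment for other variables. Annex 5 lists no session or instructor identifier.

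**The concern.** When an individually randomised intervention is delivered to groups, people taught together share the discussion, the teacher and the way the session ran. Their later results can be alike even if each is assessed alone. Because each session belongs to one arm, that shared variation does not cancel from the comparison of arms; it adds to its variance. A test that treats students as independent leaves it out, so standard errors are too small and the false-positive rate is above nominal. This affects the secondary t-tests as well as the primary outcome, and correcting only for repeated steps within a student would not remove it.

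The plan's own safeguard cannot catch the problem. Without a session identifier the dependence cannot be examined, and the usual non-parametric tests also assume independent observations. If sessions are not recorded while training is under way, they may be impossible to reconstruct later.

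**Working it through.** **1. The plan's own figure.** Inputs from Section 14: omission 26% against 16% ("treat = 0.16, control = 0.26, n = NA, power = 0.9"), and "It also establishes power of 90% and alpha of 0.05". The standard two-proportion formula, with mean proportion p = 0.21 and the squared difference in the denominator, is

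n = [z(α/2)·√(2p(1−p)) + z(β)·√(p₁(1−p₁)+p₂(1−p₂))]² / (p₁−p₂)².

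Two-sided α = 0.05 gives 347 steps per arm, not the stated 492; two-sided α = 0.01 gives 492. That mismatch is a separate matter. It is relevant here only because it leaves spare sample. The later steps do reproduce: 984 × 1.2 = 1,180.8, and divided by 21 this is 56.2, so 56 students, or 28 × 21 = 588 steps per arm. Neither 347 nor 492 contains any allowance for correlation.

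**2. Training-group effect alone.** The documents give neither m (students per session) nor the ICC (session correlation of the student-level result), so both are assumed. Design effect D = 1 + (m−1)·ICC; standard error multiplier √D; true two-sided error of a nominal 5% test = 2[1 − Φ(1.96/√D)].

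| m | ICC | D | SE multiplier | True error |
|---|---|---|---|---|
| 3 | 0.05 | 1.10 | 1.05 | 6.2% |
| 4 | 0.05 | 1.15 | 1.07 | 6.8% |
| 6 | 0.05 | 1.25 | 1.12 | 8.0% |
| 3 | 0.10 | 1.20 | 1.10 | 7.4% |
| 4 | 0.10 | 1.30 | 1.14 | 8.6% |
| 6 | 0.10 | 1.50 | 1.22 | 11.0% |

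These rows describe a test that is otherwise valid with the student as unit.

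**3. Together with steps within student.** The primary test counts 21 steps per student as independent. With within-student correlation ρ, total D = (1 + 20ρ) × (1 + (m−1)·ICC). At an assumed ρ = 0.05 the first factor alone is 2.0, larger than any row above. Multiplied by 1.10 to 1.50 it gives 2.2 to 3.0.

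**4. What the spare sample covers.** Against 347 steps per arm, 588 steps keep 90% power up to D = 588/347 = 1.69. After 20% losses, 22.4 × 21 = 470 steps keep it up to 470/347 = 1.36. Most rows in step 2 fall within this allowance, but the totals in step 3 do not. Spare sample protects power only; the width of a naive interval stays wrong by √D. These power statements are for a test of zero difference, whereas Section 20a words the null as a difference of 10% or less.

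**5. Cost of the correction.** With 28 students per arm, m = 4 gives about 14 groups in all (12 degrees of freedom, critical t 2.18) and m = 6 about 10 groups (8 degrees of freedom, critical t 2.31). A student-level test has 54 degrees of freedom and critical t 2.00. The rise is about 9% and 15%.

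**The case against.** The strongest reply is that group training is inferred, not stated. The sentence about reflection among the participants is a confidentiality rule that covers both training and outcome measurement, and at outcome measurement there is only one student in the room. Assigning someone to the checklist is a behaviour to be learned, and the plural may be generic. That is a fair reading of each phrase by itself. Taken together, and set against the explicit statement that outcome assessment is separate, shared training is still the more natural reading, but the point has to stay conditional.

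Three further limits stand.
- **Instructors.** A reader might infer that instructor effects necessarily narrow the intervals. The documents do not support this. Section 11a can be read as one trained teacher throughout, and Section 17a ties no instructor to an arm. If the same teachers serve both arms, their main effect largely cancels; they add to the problem only if they differ between arms or sessions.
- **Crises drawn.** The outcome crises must differ from those used in training, so a shared training draw acts only indirectly, through what remains available for assessment.
- **Fixed groups.** Nothing says that the same students attend together on both days. If membership changes, 1 + (m−1)·ICC does not apply as written.

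The cost of correction is also real. At ICC 0.05 the rise in critical value (9% at m = 4, 15% at m = 6) exceeds the standard-error inflation being corrected (7% and 12%), and a variance component estimated from 10 to 14 groups is imprecise.

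**Conclusion.** The concern holds conditionally. Training is arm-specific and appears to be shared, and nothing in Section 14, Table 9 or Annex 5 allows for correlation between students trained together. If sessions are shared and the session correlation is positive, the intervals for primary and secondary outcomes are too narrow. Under assumed group sizes of 3 to 6 and ICC of 0.05 to 0.10, the added variance is 10% to 50% and the true error of an otherwise valid student-level 5% test is about 6% to 11%. No figure in the documents fixes where in that range the trial lies, and if every student trained alone the group effect would vanish.

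Two stronger readings should be avoided. The documents do not establish that the intervals are too narrow by a known amount because of training groups. Nor are training groups the main source of understated error: the nesting of 21 steps within each student is certain from the design and probably larger. The point is minor in rank, but cheap to act on and hard to repair after training ends.

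**What to change.** 1. In Section 11a, state how many students attend a session, whether the same students stay together on both days, how many instructors teach, and whether they teach both arms.
2. Add training-session (for each day) and instructor identifiers to Annex 5 and record them for every student from the first session.
3. In Section 20a, replace the pooled-step chi-square with an analysis of each student's omission proportion, or a step-level model with a student effect. A training-group term cannot simply be added to the present primary test, because that test has no student level.
4. For primary and secondary outcomes, use a training-group random intercept, or training-group cluster-robust errors with a small-sample correction. If groups turn out very few, or change between the two days, keep this at least as a pre-specified sensitivity analysis.
5. Reword Section 20b so that it does not exclude these terms, and replace the design effect of 1 in Section 14 with a stated assumption.

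The cost is a few identifier fields and a revised model. The downside is fewer degrees of freedom: with about 10 to 14 groups, critical values are about 9% to 15% higher than in a student-level test.

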This possible communication can lead to biases that affect the internal validity of the study. First, compensatory rivalry bias, if the control group, in this case checklists, knows the outcome, they could behave differently to try to lessen the effect of the outcome on their group, responding to social competition.

Second, demoralization bias, for the control group knowing that they would not receive the intervention training.

To avoid these two possible biases, after recording the three crises to measure the outcome, all participants will undergo training corresponding to the other intervention arm to which they were initially assigned by means of protocol-directed reflection on non-skills. techniques for the control case or checklists for the intervention group case. Additionally, the platform of the arm opposed to the intervention will be left open to each participant.

11b. Modification of the intervention

As these are two educational strategies, no need for changes in the interventions is expected.

11c. Strategies to improve adherence

Various strategies will be used to improve adherence to the study protocol.

Firstly, participants who agree to participate in the study will be explained the importance of fully complying with the intervention and control protocol, and the voluntary nature of participation will be emphasized.

In addition, clinical internship rotations will be sought to ensure attendance at the three face-to-face sessions, two for training, one for outcome measurement, especially the course for critical patient care and the elective rotation for anesthesia for the last semester of medicine. It will seek support from the teachers who coordinate these rotations to achieve this goal.

On the other hand, the virtual platform will have an easily developed content, which meets the objectives of standardizing the technical knowledge necessary for learning to carry out the intervention and control activities. The platform will be closely watched by one of the researchers to confirm the use of it by the participants. Lastly, the simulation center of the Faculty of Medicine of the University of Antioquia will be requested the appropriate spaces for interventions and recordings to measure the outcome, seeking to be separated from other training stations and thus ensure the comfort of the participants. .

11d. Concomitant interventions

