As the teaching-learning relationship is bidirectional, other educational interventions on technical skills related to the scenarios and the resolution of questions and doubts about the technical concepts related to the platform will be allowed for both groups.

No training will be conducted in either group on non-technical skills other than those contained in the training in this protocol.

12. Outcomes

12.1 Primary outcome:

Difference of proportions of omission of steps to treatment by group, the measurement of this outcome will be made by reviewing the recordings of three random medical crises different from those used for training in each group of participants. The evaluation will be done by an independent collaborator blinded to the intervention group and previously trained in the detection of errors by one of the authors. Failure to apply the specific actions defined in each pathology, chosen by the authors according to Annex 1, will be considered as omission of the treatment step, this includes the maximum time determined for each action, the choice of appropriate medications with their respective doses, among others. Each evaluation is independent, each crisis will be evaluated in seven steps,

12.2 Secondary outcomes:

12.2a 1Difference of crisis resolution time averages in seconds between both groups, measured in the recording, taking as the beginning of the crisis the moment of calling the treatment team and the end when all the effective treatment of each crisis is completed, according to the treatment steps described in Annex 1. In the event that the treatment steps are not fully completed, the time will be measured until the end of the simulation.

12.2b Difference of time averages in detection and discrimination of the crisis in seconds between both groups, taking as the beginning of the crisis the moment of calling the treatment team and the end the moment of explicitly requesting the specific checklist for the crisis or verbalize the diagnosis of the code situation. If the specific list is not requested or the diagnosis is not verbalized, the time until the end of the simulation will be counted.

12.2c Mean difference between the global non-technical skills score measured with the Ottawa global scale based on video recording by an independent evaluator.

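### Nothing holds the other arm's training and platform back until classmates have been recorded, so non-technical-skills content could reach unrecorded controls and dilute the primary difference

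*Combined protocol and SAP*

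**What the plan says.** Section 11a, under the subheading on what happens after outcome recording, acknowledges that students of the same year at one centre cannot be blinded and that "there may be communication between treatment and control groups". It names two resulting biases, compensatory rivalry and demoralisation, and offers a single remedy for both ("To avoid these two possible biases"). That remedy is a crossover of training: "after recording the three crises to measure the outcome, all participants will undergo training corresponding to the other intervention arm". In addition, "the platform of the arm opposed to the intervention will be left open to each participant".

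Other sections bear on timing and contact:

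- Section 11c plans to "ensure attendance at the three face-to-face sessions, two for training, one for outcome measurement". Section 26 likewise tells participants of three simulation days.
- Section 15 recruits by rotation and cohort: "Explanation of the project at least once per internship cohort with the whole group". Its monitoring table has eight monthly columns.
- Section 16a randomises individuals 1:1 in blocks of 2 and 4, without strata.
- Section 11a (simulation protocol, principle 2) asks that what is done in simulation sessions "will not be commented on in other scenarios".
- Section 11d states: "No training will be conducted in either group on non-technical skills other than those contained in the training in this protocol".
- Sections 18b and 24 (item 3) present training in both interventions as a reason to stay in the study and as a matter of fairness.

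**The concern.** The plan recognises contact between arms but follows through on only two of its consequences. The third, contamination, is not named, measured or allowed for in the sample size. The remedy for the first two adds to it. Once recorded, a control student receives the non-technical-skills debriefing and an open platform, while classmates in the same rotation may still be in training or waiting to be recorded.

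Much of the content consists of short behaviours that are easy to pass on, such as calling for help early, assigning tasks and checking orders back. At least one touches a scored step directly, because requesting help within a minute is step 2 of every crisis in Annex 1. Any content that reaches unrecorded controls and works there lowers the control omission rate and shrinks the primary contrast.

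**Working it through.** **1. Does the text allow recorded and unrecorded controls to coexist?**

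- The trigger for crossover is the participant's own recording. No clause refers to the last recording of a cohort or of the trial.
- Each participant is recorded separately, on a day after training ends. Table 7 runs over about 15 days per participant.
- Enrolment is by rotation, and unstratified small blocks will generally put both arms in one cohort.
- With three face-to-face sessions, the last being the recording, no later session is set aside for the crossover debriefing.

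Overlap is therefore expected under the plan as written. Delivery on or near the recording day is an inference, though a well-supported one.

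**2. Which route matters?** Intervention students have already been taught the same checklist behaviours, so their crossover adds little. The route that matters runs from a recorded control to an unrecorded control.

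**3. Do the safeguards close it?** The confidentiality principle covers actions in the sessions. It does not mention platform material or learned behaviours. Section 11d bars non-technical-skills training outside the protocol, but the crossover is inside it. Both help only in part.

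**4. The plan's own sample size.** Inputs from section 14: control 0.26, intervention 0.16, two-sided alpha 0.05, power 90%, design = 1. The formula is

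n per arm = [z(α/2)·√(2p̄q̄) + z(β)·√(p₁q₁ + p₂q₂)]² / (p₁ − p₂)²

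With p̄ = 0.21: [1.96 × 0.5760 + 1.2816 × 0.5717]² / 0.01 = 346.6, so 347. The stated 492 is not reproduced; it appears at two-sided alpha 0.01. The later steps do follow: 492 × 2 = 984; 984 × 1.2 = 1,180.8; divided by 21 this is 56.2, so 56 students. The mismatch is a separate matter. I use 492 below because it is the plan's figure.

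**5. Illustrative dilution.** Let c be the share of the effect that reaches the control arm on average. **The documents give no value for c, so it is assumed.** The control rate becomes 0.26 − 0.10c, and d is its difference from 0.16. The null is no difference, steps are treated as independent, and

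power = Φ{[d√n − 1.96·√(2p̄q̄)] / √(p₁q₁ + p₂q₂)}, n = 492

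Example for c = 0.20: d = 0.08, p̄ = 0.20; [0.08 × 22.181 − 1.96 × 0.5657] / 0.5629 = 1.183, so power is 88.2%.

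| c (assumed) | Control rate | Difference | Power at 492 per arm | Steps per arm for 90% |
|---|---|---|---|---|
| 0 | 0.26 | 10 points | 97.2% | 347 |
| 10% | 0.25 | 9 points | 93.9% | 421 |
| 20% | 0.24 | 8 points | 88.2% | 524 |
| 30% | 0.23 | 7 points | 79.2% | 672 |

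c averages over all controls. If half were exposed before recording and each took up 20% of the effect, c would be 0.5 × 0.2 = 10%.

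**The case against.** Several points on the other side stand.

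- **Timing.** A reader might infer that the plan orders crossover immediately after recording. It does not: the wording would also fit a joint session once a cohort is finished. The participant timeline figure and the cell entries of Table 7 are not available in the text reviewed and might settle this.
- **Origin of the leak.** A reader might conclude that the crossover creates the contamination. It does not. Intervention students hold the content during training and can talk to controls before anyone is recorded. The assumed c cannot be attributed to crossover alone.
- **Strength of the leak.** The intervention is ten hours, eight of them debriefed simulation, and the protocol itself doubts the effect of a single day. Conversation, or second-hand sight of a two-hour platform, is unlikely to pass on much of it. The outcome crises also differ from the training crises, and a researcher follows platform use.
- **Power.** A reader might add clustering of the 21 steps within a student and report much lower power. With an assumed intraclass correlation of 0.10, the design effect is 1 + 20 × 0.10 = 3. The effective size is 492 / 3 = 164 and power is 60.5%, 52.4% and 44.1% at c = 0, 10% and 20%. The drop from 97.2% to 60.5% comes entirely from the correlation, which the documents do not give. It is a different issue and should not be counted as the cost of the crossover.
- **Direction.** Dilution pulls toward no difference, so it cannot produce a false claim of superiority.

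None of this removes the gap. The plan admits contact between arms and releases the experimental content to controls with no hold for those still unmeasured.

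**Conclusion.** The point holds in a limited form. As written, the plan permits, and probably leads to, recorded controls holding the non-technical-skills training and platform while other controls await recording. The result is an avoidable addition to an existing contamination risk, with bias toward zero. It rests on three assumptions: that crossover takes place on or near the recording day, that students talk as the protocol expects, and that content passed on has some effect.

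The size is unknown. On the plan's own 492 independent steps per arm, an assumed 10% or 20% leak costs 1 or 2 points of a 10-point difference and takes power from 97% to 94% or 88%. These figures describe total leakage, so the crossover's share is smaller. The power levels are also optimistic to the extent that steps within a student are correlated. The change is worth making because it is cheap, not because the documents show a large effect.

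**What to change.** In section 11a, under what follows outcome recording, state that:

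1. the other arm's platform is opened, and the crossover training delivered, only after the last participant of that internship or rotation cohort has been recorded;
2. training in both arms remains guaranteed to every participant, so that the retention benefit in section 18b and the fairness commitment in section 24 are kept;
3. participants are reminded not to share platform content with students who have not yet been recorded.

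Show the crossover date in the participant timeline and Table 7.

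Cost: some students wait longer and may need a separate session beyond the three now planned. Outcome data already recorded are unaffected, and no sample-size figure changes. What remains is leakage from one cohort to the next and from intervention students during training, which this change does not address.
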